4.2.2. Exclusion Criteria

Deviations from exclusion criteria are not allowed because they can potentially jeopardize the scientific integrity of the study, regulatory acceptability or subject safety. Therefore, adherence to the criteria as specified in the protocol is essential.

Subjects meeting any of the following criteria must not be enrolled in the study:

Safety

1. The subject has a mixed malaria infection (identified by a malarial smear or rapid diagnostic test).
2. The subject has severe *P. vivax* malaria as defined by WHO criteria.
3. The subject has a history of allergy to chloroquine, mefloquine, tafenoquine, primaquine, or to any other 4- or 8-aminoquinoline.

Hepatic Disease

4. The subject has a liver ALT >2 x ULN.

Concurrent Disease

5. The subject has severe vomiting (no food or inability to take food during the previous 8 hours).
6. The subject has a clinically significant concurrent illness (e.g., pneumonia, septicemia), pre-existing condition (e.g., renal disease, malignancy), condition that

may affect absorption of study medication (e.g., vomiting, severe diarrhea), or clinical signs and symptoms of severe cardiovascular disease (e.g., uncontrolled congestive heart failure, severe coronary artery disease).

7. The subject has a history of porphyria, psoriasis, or epilepsy.
8. The subject has a history of significant ocular disease (e.g. surgery to the globe, glaucoma, diabetic retinopathy) or has evidence of corneal or retinal abnormalities identified in the clinical screening ophthalmologic examination.

Concurrent Medication

9. The subject has taken anti-malarials (e.g., artemisinin-based combination therapies, mefloquine, primaquine, or any other 4- or 8-aminoquinoline) within 30 days prior to study entry.
10. The subject has taken or will likely require during the study the use of medications from the following classes:

- Histamine-2 blockers and antacids
- Drugs with hemolytic potential
- Drugs known to prolong the QTcF interval
- The biguanides phenformin and buformin (but excluding metformin)
- Drugs that are substrates of the renal transporters OCT2, MATE1 and MATE-2K and have a narrow therapeutic index (for example, the anti-arrhythmic agents dofetilide, procainamide and pilsicainide)

Other

11. The subject has received treatment with any investigational drug within 30 days of study entry, or within 5 half-lives, whichever is longer.

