5.6.2. Prohibited Medications and Non-Drug Therapies

The following drugs are prohibited for use from 30 days prior to entry in the study through Day 180:

- Anti-malarials and other medicines with known anti-malarial activity.
- Drugs with hemolytic potential.
- Drugs known to prolong QTcF
- Drugs known to interact with primaquine or chloroquine.

Results from an *in vitro* renal transporters study showed that TQ inhibits the renal transporters MATE1, MATE2-K AND OCT2. Inhibition of these transporters may explain mild, transient, asymptomatic increases of creatinine observed in previous clinical studies and may lead to increased exposure to medications excreted via these transporters. The following drugs are prohibited for a period of 21 days immediately following the blinded dose of tafenoquine.

- The following anti-diabetic drugs of the biguanide class:
 - Phenformin
 - Buformin
- The following anti-arrhythmic drugs:
 - Dofetilide
 - Procainamide
 - Pilsicainide

Metformin, another biguanide anti-diabetic, may continue to be taken provided the subject has serum creatinine below the upper limit of normal and has no concomitant medical condition that increases the risk of lactic acidosis.

The use of herbal remedies during the course of the study is to be avoided. However, if taken this should be recorded in the eCRF under concomitant medication.

See [Appendix 5](#) in Section 11.5 for a non-exhaustive list of prohibited medicines for guidance.

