13.1. Appendix 1: Protocol Deviation Management and Definitions for Per Protocol Population

13.1.1. Protocol deviations

Major protocol violations could impact the ability to assess efficacy and our primary endpoints for our study. A subject meeting any of the following criteria will be excluded from the Per Protocol population:

Number	Exclusion Description
1	Subject does not have a parasitology assessment within window for any of the Day 2, Day 3, Day 29, Day 60, Day 90, Day 120, Day 150 or Day 180 visits
2	Subject does not demonstrate initial parasite clearance but does not receive rescue medication
3	When in the clinic on Day 1 to 3, subject vomited a dose of study medication and either vomited the redose, or a redose was not given
4	PQ/PQ placebo pill count suggests that the subject failed to take two or more scheduled doses when away from the clinic
5	Violation of any of the following entry criteria: 
 • Subject had a mixed malaria infection at baseline • Subject had an asexual P. vivax parasite count ≤ 100 or ≥ 100000 • Subject had a severe malaria infection • Subject had severe vomiting or diarrhoea • Subject had taken anti-malarials within the previous 30 days
6	The subject has taken/received: 
 • anti-malarials (e.g., artemisinin-based combination therapies, mefloquine, primaquine, or any other 4- or 8-aminoquinoline) within 30 days prior to study entry. • treatment with any investigational drug within 30 days of study entry, or within 5 half-lives, whichever is longer. • a concomitant medication with an anti-malarial activity between Day 1 and the Day 180 visit, and remained parasite negative throughout the study. A list of all concomitant medications will be reviewed by a GSK clinician prior to unblinding the study, and classified accordingly

NOTES:

- A listing will be produced for the PP population showing
 1. individual subject numbers for each protocol violation
 2. the number and percentage of subjects for each violation
 3. the total number of subjects with one or more violation will be tabulated, by type of violation.

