13.6.2. Study Population

Demographics

Age

- Only the year of birth is collected in the eCRF and the day and month are imputed as ‘30th June’.
- GSK standard IDSL algorithms are used to calculate age at baseline.
- Birth date will be presented in listings as ‘YYYY’.
- Age on the date of first dose will be calculated in years.

Prior and Concomitant Medications

- Medications will be coded using the latest version of GSK Drug.
- Prior medications = medications taken up to 30 days before the date and time of the first dose of study medication.
- Any medications with stop dates earlier than 30 days will not be reported in tables and listings.
- Concomitant medications = medications with start date and time on or after the start date and time of the first dose of study medication (Study Day 1).
- See Section [13.7.2](#) for the handling of missing and partial dates.

Treatment Compliance and Exposure

- For the first three days of the study, all study medication will be administered in the presence of the Investigator or study nurse, and ingestion confirmed.
- On any day of in clinic dosing, a subject will be classified as compliant with daily administered dose if they do not vomit the initial dose or if they are successfully re-dosed.
- A subject is considered to be compliant in clinic if they retain all study medication given to them on all three days of dosing.
- Subjects will also take PQ or PQ placebo on Study Days 4 to 15, where administration is not directly observed (with the exception of G6PD-deficient subjects, who will receive directly-observed therapy on all 15 days).
- A patient will be considered to be compliant as an outpatient if their final pill count data shows they took at least 12 doses of PQ or PQ placebo.
- Compliance will also be determined using the Day 8 and Day 15 PK samples i.e. a quantifiable amount of carboxyPQ from samples taken at the Day 8 and Day 15 visits. No assessment windows will be applied.
- Subjects who were randomized but did not report a treatment start date will be categorised as having zero doses.
- Treatment stop dates are not recorded so duration of exposure will not be calculated.

G6PD enzyme activity as a percentage of site median

- Each site has a median G6PD enzyme value for healthy G6PD-normal subjects, determined from G6PD-normal males in study TAF115226:

Region	Country	Site	Investigator	Centre ID	G6PD median value (IU/g Hb)
South America	Brazil	Manaus	[name]	PPD	7.92
	Peru	Iquitos	[name]		9.01

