13.6.4. Efficacy**Relapse free efficacy and Time to Relapse****Six months**

- A subject will be considered to have demonstrated relapse-free efficacy at 6 months for the purposes of the analysis if **all** of the following are true (also described in the flowchart below):
 - Subject had a non-zero *P. vivax* asexual parasite count at baseline. Subjects with no asexual *P. vivax* parasites at this time point will be censored with time to relapse = 0 days.
 - Subject demonstrated initial clearance of *P. vivax* parasitaemia. This is defined as two negative asexual *P. vivax* parasite counts, with at least 6 hours between the counts, and no positive counts in the interval. Subjects who do not meet this criteria will be classified as relapses, with time to relapse = 0 days.
 - Subject has no positive asexual *P. vivax* parasite count at any assessment prior to or on Study Day 201 following initial parasite clearance. Subjects who do have a positive count will be classified as relapses, with time to relapse = (date of first positive count) – (date of Study Day 1) days.
 - Subject did not take a concomitant medication with anti-malarial activity at any point between Study Day 1 and their last parasite assessment. A list of all concomitant medications will be reviewed by a GSK clinician prior to unblinding the study, and classified accordingly. Subjects who did take a drug with anti-malarial activity but never had a positive asexual *P. vivax* parasite count after initial clearance will be censored, with time to relapse censored at (date of last negative parasite assessment prior to concomitant medication start) – (date of Study Day 1). If a subject has not had a negative assessment prior to the concomitant medication start date, they will be censored at 0.
 - Subject is parasite-free at 6 months. This is defined as a negative asexual *P. vivax* parasite count at the first parasite assessment performed on or after Study Day 166.
- Subjects who do not have a positive asexual *P. vivax* parasite count following initial clearance but where the final parasite count occurred before Study Day 166 will not have been classified by the preceding rules. These subjects will be considered to be censored, with time to relapse censored at (Date of final parasite assessment) – (date of Study Day 1).

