13.7.2.2. Handling of Partial Dates

Element	Reporting Detail
Concomitant Medications	
 Partial dates for any concomitant medications recorded in the CRF will be imputed using the following convention: 
 If the partial date is a start date, a '01' will be used for the day and 'Jan' will be used for the month If the partial date is a stop date, a '28/29/30/31' will be used for the day (dependent on the month and year) and 'Dec' will be used for the month. The recorded partial date will be displayed in listings.
Adverse Events	
 It is not possible to record partial dates in the eCRF for AEs.
Date of birth	
 Where a subject's date and month of birth is not known, the investigator has been asked to enter them as 30th June, and where month is known but date is unknown, the investigator has been asked to enter the 15th. Thus all subjects should have an actual or an assumed date of birth entered on the eCRF. In the event that any partial dates do occur for date of birth, age should be calculated using 30th June for an unknown date and month, and 15th for an unknown date only. Only the year will be displayed in listings.

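### The RAP defines concomitant medication by start date alone, so a drug with anti-malarial activity begun before first dose and continued on study can escape the mITT relapse rules and, for one drug class, Per Protocol exclusion

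*Supplement*

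**What the plan says.** RAP Amendment 1, Section 13.6.2, gives two definitions: "Prior medications = medications taken up to 30 days before the date and time of the first dose of study medication" and "Concomitant medications = medications with start date and time on or after the start date and time of the first dose of study medication". Neither mentions a drug that starts before first dose and continues afterwards.

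The efficacy rules depend on the second definition. For six-month relapse-free efficacy, Section 13.6.4 requires: "Subject did not take a concomitant medication with anti-malarial activity at any point between Study Day 1 and their last parasite assessment". A subject who breaks this and stays parasite-negative is censored at the last negative smear before the drug started, and: "If a subject has not had a negative assessment prior to the concomitant medication start date, they will be censored at 0". The four-month rule, the three missing=failure definitions and the recrudescence censoring rule use the same term. The clinician's review before unblinding is of a list of concomitant medications. Section 13.1.1 item 6, third bullet, excludes from Per Protocol (PP) a subject who took "a concomitant medication with an anti-malarial activity between Day 1 and the Day 180 visit, and remained parasite negative throughout the study".

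Protocol Amendment 5, Section 5.6.2, prohibits "Anti-malarials and other medicines with known anti-malarial activity" from 30 days before entry through Day 180. Appendix 5 lists the two classes separately. Exclusion criterion 9 names only the first: "The subject has taken anti-malarials (e.g., artemisinin-based combination therapies, mefloquine, primaquine" and other 4- or 8-aminoquinolines.

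**The concern.** The censoring and failure rules exist because another drug active against the parasite can suppress a relapse that would otherwise have been seen. What matters is whether the drug was being taken between Study Day 1 and the last smear, not when it was started. Under the start-date definition, a subject who entered on such a drug and continued it can be analysed as relapse-free for the whole follow-up. The drug may also never reach the clinician who classifies medications.

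At stake are this study's secondary efficacy endpoints and, because Section 8.2 of the Meta-Analysis Plan uses the same derivation, the pooled non-inferiority comparison.

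**Working it through.** **Rule trace.** Take a drug with anti-malarial activity that has a known start before first dose and a known stop on study, in a subject who stays parasite-negative.

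| Rule | Result |
|---|---|
| 13.6.2 classification | Prior only |
| 13.6.4 censoring, six and four months | Not triggered; subject counts as relapse-free |
| 13.6.4 missing=failure definitions | Not triggered by the drug |
| 13.6.4 recrudescence censoring | Not triggered |
| Clinician's review list | Need not include the drug |
| 13.1.1 items 5 (last bullet) and 6 (first bullet), drug is an anti-malarial | Triggered: a drug still in use at entry was taken in the previous 30 days, so the subject leaves PP |
| 13.1.1, drug is only in Appendix 5's antimalarial-activity list (e.g. clindamycin, isoniazid, rifampicin, glibenclamide) | Not triggered; subject stays in PP |

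The clause that censors at 0 would suit a drug already running at Day 1, but it is not reached because the drug is not concomitant.

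**Intended meaning.** Protocol Section 5.6.1.1 asks for all concomitant medications taken during the study. RAP Section 2.1, which lists departures from the protocol's analysis, does not mention a narrower definition. The censoring rule's own period starts at Study Day 1 and concerns taking the drug. At the least, rule and definition conflict.

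**Partial dates.** In RAP Section 13.7.2.2, the rule beginning "If the partial date is a start date" supplies day 01 and month January. As an illustration, let first dose be 15 June and let a drug start on 25 June but be recorded only as June. The imputed start is 1 June, so the drug becomes prior. With only the year known, the imputed start is 1 January. The error therefore needs a true start in the same month as Day 1, or the same year if only the year is known. Elsewhere the RAP resolves doubt towards inclusion: medications with missing dates and missing flags are taken as concurrent, and adverse events of unknown onset as treatment-emergent.

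**Missing dates.** Section 13.7.2.1 sends a record whose start or stop date is entirely unknown to the eCRF flags for use before the study and for ongoing use. It does not say how a drug with both flags set is classified.

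**Size.** The documents give no count of such subjects, so only a per-subject effect can be shown. Inputs:
- 251 randomised (Meta-Analysis Plan Section 3) at 2:1, so about 167 and 84; the split is assumed.
- Primaquine efficacy p = 60.3%, one of the values in Meta-Analysis Plan Section 9.1; assumed to apply here.
- 214 primaquine subjects expected in the pooled data (same section).

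Treat the six-month rate as a simple proportion with no other censoring. Removing k relapse-free subjects from n at time 0 lowers it by k(1 − p)/(n − k):
- n = 84, k = 1: 0.397/83 = 0.48 points.
- n = 84, k = 3: 1.191/81 = 1.47 points.
- n = 214, k = 1: 0.397/213 = 0.19 points.
- n = 214, k = 3: 1.191/211 = 0.56 points.

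Under missing=failure the subject moves from success to failure, so the shift is 1/84 = 1.2 points in the primaquine arm and 1/167 = 0.6 points in the tafenoquine arm.

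**The case against.** The case on the other side is that the clear gap is narrow.

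- **Drugs still being taken at study end.** These would normally have no stop date and so go to the flags. This stands: the unambiguous failure is a drug with a known on-study stop date. It also means one cannot say that the concomitant-medication table (Table 1.12) omits every ongoing drug. Table 1.11 and Listing 24 would still show drugs started earlier.
- **Per Protocol.** A reader might infer that such a drug never leads to PP exclusion. The documents do not support that: items 5 and 6 (first bullet) remove subjects with anti-malarials in the previous 30 days, whatever counts as concomitant. The second class remains exposed.
- **Entry.** Section 5.6.2 and Appendix 5 already bar this class, criterion 10 stops some listed drugs, criterion 6 may exclude some patients through the underlying illness, and important deviations are reviewed before unblinding. This makes cases fewer, but does not tell the analysis what to do with one. With 251 subjects already randomised, rewording criterion 9 would change nothing.
- **Size.** A reader might set 1.2 to 3.6 points (one to three of 84) against the 6.5 to 9.1 points to which the margin translates in Meta-Analysis Plan Table 2. That is not a fair comparison. Those shifts treat each subject as a failure, whereas the main analysis would censor at 0, and the margin applies to the pooled data.
- **Direction.** A reader might infer that the gap pulls the arms together. That would need similar misclassification in both arms. If the cases were all on primaquine, primaquine would look better and non-inferiority would be harder to show. The documents do not settle it.

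**Conclusion.** The definition in RAP Section 13.6.2 does not do what Section 13.6.4 needs. A drug with anti-malarial activity begun before first dose and continued on study, clearly so when its on-study stop date is known, does not trigger the mITT censoring, missing=failure or recrudescence rules. In PP the gap is confined to Appendix 5's other drugs with antimalarial activity. The partial-date rule adds a further route, and the flag rule leaves one combination undefined.

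The effect per subject is small: about 0.5 points on the primaquine six-month rate here and about 0.2 points in the pooled primaquine arm, under the assumptions stated above. The number of subjects and the direction of bias are unknown. The reach is secondary efficacy in this study and the pooled non-inferiority analysis, whose primary PP population is taken from the studies. The primary haemolysis endpoint is not touched. The change is worth making because it is cheap and the present text can label subjects relapse-free against the rule's evident purpose.

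**What to change.** Before unblinding, amend the RAP:

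1. **13.6.2:** define concomitant as any medication with a stop date and time on or after first dose, or flagged ongoing, whatever its start. A drug may be both prior and concomitant. This also settles the case where both eCRF flags are set.
2. **Carry it through** to 13.6.4, 13.1.1 item 6, Table 1.12 and the clinician's review list. A drug already running at Day 1 then meets the existing rule for censoring at 0.
3. **13.7.2.2:** treat a partial start date compatible with on-study use as concomitant, and state which date is used for censoring, since an imputed start before Day 1 would otherwise force censoring at 0.
4. **13.1.1 item 6, first bullet:** extend it to medicines with known anti-malarial activity, so that it matches protocol Section 5.6.2.

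The cost is RAP wording and one derivation. The plan already relies on stop dates and the ongoing flag, so no new data are needed. A few more subjects will be censored, counted as failures in the sensitivity analyses, or excluded from PP. No change to the entry criteria is needed.

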5.1.7. Duration of Treatment of Active Study Medication

The total duration of treatment is 15 days.

Chloroquine will be dosed orally once daily for three days starting on Day 1 of the study.

Tafenoquine will be dosed orally as a single dose on Day 1 or Day 2 of the study.

Primaquine will be given as a 14-dose course administered orally once daily for 14 days starting from Day 1 or Day 2 of the study.

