5.1.8. Dose and Administration

Study medication should be administered with food. If the subject vomits within 1 hour following dosing, a repeat dose should be given. If a subject sequentially vomits two doses of study medication he/she will be considered intolerant to study medication. These subjects will be withdrawn from study medication and be given appropriate rescue medication as outlined in Section 5.6.1.2. Subjects and all site staff will be blinded to the study treatment.

Subjects will be randomized into one of two treatment arms. Subjects that receive the 500 mg CQ tablet (300 mg CQ free base) will receive the following number of CQ tablets, TQ/placebo tablets and PQ/placebo capsules:

Treatment Arm	Day 1	Day 2	Day 3	Days 4 – 15
tafenoquine	2×CQ 300mg	2×CQ 300mg + 2×TQ 150mg + 1×PQ placebo	1×CQ 300mg + 1×PQ placebo	1×PQ placebo
primaquine	2×CQ 300mg	2×CQ 300mg + 2×TQ placebo + 1×PQ 15mg	1×CQ 300mg + 1×PQ 15mg	1×PQ 15mg
Total number of capsules/tablets per treatment arm	2 tablets	4 tablets + 1 capsule	1 tablet + 1 capsule	1 capsule × 12 days

NOTE: subjects may begin blinded study medication (TQ or PQ and corresponding placebo) on Day 1 or Day 2 of the study.

Subjects that receive the 250 mg CQ tablet (155 mg CQ free base) will receive the following number of CQ tablets, TQ/placebo tablets and PQ/placebo capsules:

Treatment Arm	Day 1	Day 2	Day 3	Days 4 – 15
tafenoquine	4×CQ 155mg	4×CQ 155mg + 2×TQ 150mg + 1×PQ placebo	2×CQ 155mg + 1×PQ placebo	1×PQ placebo
primaquine	4×CQ 155mg	4×CQ 155mg + 2×TQ placebo + 1×PQ 15mg	2×CQ 155mg + 1×PQ 15mg	1×PQ 15mg
Total number of capsules/tablets per treatment arm	4 tablets	6 tablets + 1 capsule	2 tablet + 1 capsule	1 capsule × 12 days

NOTE: subjects may begin blinded study medication (TQ or PQ and corresponding placebo) on Day 1 or Day 2 of the study.

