6.6.2. Pharmacokinetic/Pharmacodynamic Sample Analysis

Plasma sample analysis will be performed under the management of PTS-DMPK/Scinovo, , GlaxoSmithKline. Concentrations of TQ will be determined using the currently approved analytical methodology. In addition, concentrations of CQ and desethylchloroquine will be determined in both treatment arms of the study. PQ and carboxy-PQ levels will be measured from the PK samples collected on Days 1-3, Day 8 and Day 15. If the actual collection day of the Day 15 sample is later than Day 15, PQ/carboxy-PQ levels will not be assessed. Raw data will be archived at the bioanalytical site (detailed in the Study Procedures Manual).

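### The 12-dose cut-off for outpatient primaquine compliance ignores the permitted Day-1 start and does not match the per-protocol pill-count rule under either reading

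*Supplement*

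**What the plan says.** Protocol amendment 5, section 5.1.7, describes primaquine (PQ) as a "14-dose course administered orally once daily for 14 days starting from Day 1 or Day 2". A note under the dosing tables in 5.1.8 repeats that "subjects may begin blinded study medication (TQ or PQ and corresponding placebo) on Day 1 or Day 2 of the study". The tables themselves are drawn for a Day-2 start and show "1 capsule × 12 days" for Days 4 to 15.

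The amended RAP (21 February 2017), section 13.6.2, separates in-clinic from outpatient dosing: "For the first three days of the study, all study medication will be administered in the presence of the Investigator or study nurse". It then places the remaining PQ or PQ placebo on Study Days 4 to 15 and calls a patient "compliant as an outpatient if their final pill count data shows they took at least 12 doses of PQ or PQ placebo". RAP 6.6 reports outpatient compliance in Table 1.21 in two categories, split between 11 and 12 doses. RAP 13.14.3 lists that table as a headline output, without the PK rows.

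The per-protocol (PP) definition in RAP 13.1.1 has its own pill-count rule. Criterion 4 removes a subject when the "PQ/PQ placebo pill count suggests that the subject failed to take two or more scheduled doses when away from the clinic".

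Table 1.21 will also show PK compliance, from carboxyPQ at Day 8, at Day 15, at either and at both. RAP 13.6.2 applies no assessment window to these samples. Protocol 6.6.2 says: "If the actual collection day of the Day 15 sample is later than Day 15, PQ/carboxy-PQ levels will not be assessed".

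**The concern.** The number 12 appears to come from a schedule that holds only for a Day-2 start. A Day-1 starter finishes one day earlier and has one dose fewer to take at home. A fixed cut-off of 12 therefore does not mean the same thing for both groups, and the RAP does not say whether it counts outpatient capsules or the whole course. A programmer would have to guess.

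At stake is how adherence to PQ or its placebo is described. The protocol's background presents poor adherence to the 14-day regimen as the main weakness of PQ, so readers will look at this table. An adherent subject placed in the lower category, or a table that disagrees with the PP rule without explanation, would mislead them.

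**Working it through.** **Inputs.** Course length 14 doses, once daily, start day s = 1 or 2 (protocol 5.1.7 and 5.1.8). In-clinic days 1 to 3 (RAP 13.6.2). Cut-off 12 doses (RAP 13.6.2 and 6.6). PP exclusion at two or more missed outpatient doses (RAP 13.1.1). The share d of subjects starting on Day 1 is not in the documents.

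**Step 1: outpatient doses by start day.** In-clinic doses = 4 − s, so outpatient doses = 14 − (4 − s).

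- Day-2 start: 14 − 2 = 12 (Days 4 to 15). This reproduces the protocol's 12 capsules.
- Day-1 start: 14 − 3 = 11 (Days 4 to 14).

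**Step 2: apply the cut-off under each reading**, with all in-clinic doses retained, and compare with PP criterion 4.

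| Start | Outpatient doses missed | Outpatient taken | Course total | At least 12 outpatient? | At least 12 in total? | Kept by criterion 4? |
|---|---|---|---|---|---|---|
| Day 1 | 0 | 11 | 14 | no | yes | yes |
| Day 1 | 1 | 10 | 13 | no | yes | yes |
| Day 1 | 2 | 9 | 12 | no | yes | no |
| Day 2 | 0 | 12 | 14 | yes | yes | yes |
| Day 2 | 1 | 11 | 13 | no | yes | yes |
| Day 2 | 2 | 10 | 12 | no | yes | no |

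On the outpatient reading no Day-1 starter can reach 12, and a Day-2 starter with one missed dose fails the table but stays in PP. On the whole-course reading every subject with exactly two missed outpatient doses passes the table but leaves PP. Neither reading agrees with criterion 4.

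**Step 3: possible size on the outpatient reading.** With perfect adherence, reported compliance = 1 − d: 90%, 75% and 50% for assumed d of 10%, 25% and 50%.

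For illustration, assume each outpatient dose is taken independently with probability 0.98.

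- Day-2 starters classed compliant: 0.98^12 = 0.785. Day-1 starters: 0.
- Overall: (1 − d) × 0.785 = 78.5% at d = 0, 58.9% at 25%, 39.2% at 50%.
- Meeting criterion 4, Day 2: 0.98^12 + 12 × 0.02 × 0.98^11 = 0.977. Day 1: 0.98^11 + 11 × 0.02 × 0.98^10 = 0.980.

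Under this assumption about 98% satisfy criterion 4 whatever d is, while the table could show a much lower figure. On the whole-course reading the table would show at least 99.8% under the same assumption, slightly above the criterion-4 figure.

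**Step 4: PK rows.** The Day 15 analysis window runs to Study Day 17 (RAP 13.3.1). A sample taken on Day 16 or 17 is within it but is not assayed for carboxyPQ. The RAP does not say whether such a subject counts as non-compliant or as missing in the rows that use Day 15. It also does not restrict the PK rows to the PQ arm.

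**The case against.** The whole-course reading is open. The upper category of Table 1.21 has no ceiling, which suits a count that can exceed 12, and outpatient doses never can. On that reading Day-1 starters can comply. This stands as a reason not to say that the cut-off is unattainable outright. Against it, the rule defines outpatient compliance, directly follows the sentence on Days 4 to 15, and sits beside a separate in-clinic summary. The outpatient reading is therefore the more natural one, though the text does not settle it.

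A reader might infer more than the documents support:

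- **The headline figure will be wrong.** That depends on the reading and on the Day-1 share. If everyone starts on Day 2 the cut-off is attainable. Even on the outpatient reading only adherent Day-1 starters are misplaced; those who missed too many doses are rightly non-compliant.
- **The table contradicts the PP rule.** A descriptive flag and an exclusion rule may legitimately differ. This is an unexplained one-dose mismatch.
- **The PP or primary results are affected.** Criterion 4 counts scheduled doses missed and does not refer to the flag. The primary haemolysis analysis does not use it either.
- **The meta-analysis inherits the fault.** Section 8.2 of that plan speaks of 14 days of dosing in total and contains neither the 12-dose cut-off nor Days 4 to 15. Its table shells are in a separate document that is not shown.
- **The PK rule distorts the headline table.** The headline version omits PK data, and the Day 8 row needs no Day 15 result.

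**Conclusion.** The point holds in a limited form. RAP 13.6.2 and 6.6 set a compliance threshold from a Day-2 schedule while the protocol permits a Day-1 start, and under neither reading does the threshold match PP criterion 4. On the more natural reading, fully adherent Day-1 starters appear in the lower category of a headline table, and Day-2 starters are allowed no missed dose.

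The size cannot be fixed from the documents. On the outpatient reading with full adherence it equals the Day-1 share; on the whole-course reading it is a one-dose difference from PP for all starters. The figures above rest on assumed Day-1 shares of 0 to 50%, an assumed per-dose adherence, and in-clinic dosing ending on Day 3. The consequence is confined to a descriptive table, so this is a minor correction worth making because it is cheap.

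**What to change.** In RAP 13.6.2, derive the number of scheduled outpatient doses from the actual start day of the PQ or PQ placebo course (not of chloroquine): 11 for a Day-1 start and 12 for a Day-2 start. Class a subject as compliant if no more than one scheduled outpatient dose is missed, that is at least 10 of 11 or 11 of 12. Replace the split between 11 and 12 in RAP 6.6 and Table 1.21 with this definition, and use the same derived variable for PP criterion 4. If the sponsor wants a different threshold in the table, the RAP should state whether it counts outpatient or total doses and why it differs from criterion 4.

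As a minor addition outside the headline version, base the Day 15 PK compliance rows on PQ-arm subjects with an assayed sample, and show the number without one.

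The cost is a few lines of derivation wording and programming; the RAP already relies on treatment start dates and final pill counts. Nothing in the dosing schedule changes.
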